### 15.12.5. Efficacy Tables

Efficacy: Tables					
No.	Population	IDSL / Example Shell	Title	Programming Notes	Deliverable [Priority]
Clinical Efficacy – Continuous endpoints					
2.1.	PPI	PD1	Summary of Mayo Score by Endpoint – Induction Phase Per Protocol Analysis	Produce table by absolute and change from baseline for the following endpoints: Complete Mayo score, Adapted Mayo Score and Partial Mayo Score for each relevant timepoint (partial Mayo reported more frequently)  Change from shell: replace SD with SE on shell	None

Efficacy: Tables					
No.	Population	IDSL / Example Shell	Title	Programming Notes	Deliverable [Priority]
2.2.	ITTE	PD1	Summary of Mayo Score by Endpoint in Induction Phase - Observed	Produce table by absolute and change from baseline for the following endpoints:  Complete Mayo score, Adapted Mayo Score, Adapted Mayo Endoscopic Score and Partial Mayo Score for each relevant timepoint (partial Mayo reported more frequently)  Change from shell: replace SD with SE on shell	SAC
2.3.	ITTE ETP	PD1	Summary of Mayo Score by Endpoint – Extended Treatment Phase	Endpoints as above.  Change from shell: replace SD with SE on shell	None
2.4.	ITTE ETP	PD1	Summary of Mayo Score by Endpoint – Extended Treatment Phase (by Induction Dose)	Condition ETP efficacy summaries on induction treatment dose.  Endpoints as above.  Change from shell: replace SD with SE on shell	None
2.5.	ITTE_OL_I	PD1	Summary of Mayo Score by Endpoint – Open Label Induction	Endpoints as above.  Change from shell: replace SD with SE on shell	None
2.6.	ITTE_OL_ETP	PD1	Summary of Mayo Score by Endpoint – Open Label Extended Treatment Phase	Change from shell: replace SD with SE on shell	None

Efficacy: Tables					
No.	Population	IDSL / Example Shell	Title	Programming Notes	Deliverable [Priority]
2.7.	ITTE	PD1	Summary of Daily Diary Scores at Selected Timepoints in Induction Phase	By endpoint Every third day from Study Day 3 until Study Day 21, then every week i.e. Day 28, 35, 42, 56, 63, 70) Endpoints: Stool Frequency sub-score Rectal Bleeding sub-score	SAC
2.8.	ITTE	PD1	Summary of UCEIS Total Score in Induction Phase - Observed		SAC
2.9.	ITTE ETP	PD1	Summary of UCEIS Total Score – Extended Treatment Phase		None
2.10.	ITTE_OI_I	PD1	Summary of UCEIS Total Score – Open Label Induction		None
2.11.	PPI	EFF_T1	Statistical Analysis of Dose Response Relationship for Complete Mayo Score – Per Protocol Population		None
2.12.	ITTE	EFF_T1	Statistical Analysis of Complete Mayo Score in Induction Phase	SAC: Change from Baseline in Complete Mayo Score at Week 10	SAC
2.13.	ITTE	EFF_T1	Statistical Analysis of Dose Response Relationship for Mayo Score by subgroup in Induction Phase	Complete Mayo Score only Subgroups: 
 
• Advanced therapy experience
 
•
 
• Race
 
• Race2
 
•
 
	None

Efficacy: Tables					
No.	Population	IDSL / Example Shell	Title	Programming Notes	Deliverable [Priority]
2.14.	ITTE	PRO_T02	Statistical Analysis of Absolute and Change from Baseline in Partial Mayo Score in Induction Phase	By Endpoint then visit Note: Repeated measures, Bayesian	SAC
Corticosteroid use					
2.15.	ITTE_ETP	EFF_T06	Summary of Corticosteroid Use After Mandatory Taper in Extended Treatment Phase	Add footnote: "Note: Average Daily Prednisolone Equivalent Dose is calculated from the start of the taper to the end of the study phase. Note that the taper starts at Week 12 and the Extended Treatment Phase (ETP) starts at Week 14. Subjects that start the taper but don't start the ETP are not included in this summary and are listed separately"	None
2.16.	ITTE_OLETP	EFF_T6	Summary of Corticosteroid Use After Mandatory Taper in Open Label Extended Treatment Phase	Add footnote: "Note: Average Daily Prednisolone Equivalent Dose is calculated from the start of the taper to the end of the study phase. Note that the taper starts at Week 24 and the Open Label Extended Treatment Phase (OLETP) starts at Week 26. Subjects that start the taper but don't start the OLETP are not included in this summary and are listed separately"	None

Efficacy: Tables					
No.	Population	IDSL / Example Shell	Title	Programming Notes	Deliverable [Priority]
Clinical Efficacy – Categorical Endpoints					
2.17.	ITTE	EFF_T2	Summary of Categorical Efficacy by Endpoint in Induction Phase - Observed	
Report by endpoint, visit. Report the endpoints below at different interims.
 
Additionally, report summaries by each level of advanced therapy experience' and 'all'
 
Endoscopic Improvement, Clinical Remission (Adapted Mayo), Symptomatic Remission, Endoscopic Remission
	IA3H, SAC
2.18.	ITTE ETP	EFF_T2	Summary of Categorical Efficacy by Endpoint in Extended Treatment Phase	
Report by endpoint, visit.
 
Include the following ETP only endpoints:
 
 
• Maintained Clinical Response (Week 10 to 30 Adapted Mayo)
 
• Maintained Clinical Remission (Week 10 to 30 Adapted Mayo)
 
• Steroid Free Clinical Remission
 
• Maintained Steroid Free Clinical Remission
 
	None
2.19.	ITTE_OL_I	EFF_T2	Summary of Categorical Efficacy by Endpoint in Open Label Phase	Report by endpoint, visit.	None
2.20.	ITTE_OL_ET P	EFF_T2	Summary of Categorical Efficacy by Endpoint in Open Label Extended Treatment Phase	
Report by endpoint, visit.
 
 
•
 
	None

Efficacy: Tables					
No.	Population	IDSL / Example Shell	Title	Programming Notes	Deliverable [Priority]
2.21.	ITTE	EFF_T7	Statistical Analysis of Categorical Efficacy in Induction Phase	
Report the endpoints below, Induction phase only:
 
Endoscopic Improvement, Clinical Remission
 
Also report estimate for each level of 'Advanced Therapy experience' (i.e. subgroup)
	IA3H, SAC
2.22.	ITTE	EFF_T7	Statistical Analysis of Categorical Efficacy in Induction Phase – Sub Group	
Endoscopic Improvement and Clinical Remission only.
 
Subgroup for each level of stratification factor (advanced therapy experience)
 
Full population:
 
 
Subgroup Race and Race2
 
 
Sub-population of biologic experience:
 
 
Biologic experience type
 
 
Sub-population of TNF failure
 
 
TNF failure mechanisms
 
•
 
	None

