### 8.1.1.2. Statistical Analysis

Bayesian analysis for continuous endpoint	
Endpoints	Change from baseline in Complete Mayo Score at Week 10
Statistical analysis	Linear regression
Predictors	
 
● TRT = study treatment(categorical)
 
● Advanced Therapy Experience (categorical) (includes interaction with study treatment)
 
● Baseline Complete Mayo (continuous)
 
● Duration of disease, years (continuous)
 

Model	$y_i \sim \text{Normal}(\text{mean}=\mu, \text{SD}=\sigma)$ $\mu = (\text{TRT=Placebo}) \times (\text{Experienced}=Y) \times \beta_1 +$ $(\text{TRT}=450\text{mg}) \times (\text{Experienced}=Y) \times \beta_2 +$ $(\text{TRT=Placebo}) \times (\text{Naive}=Y) \times \beta_3 + (\text{TRT}=450\text{mg}) \times (\text{Naive}=Y) \times \beta_4$ $+ (\text{Duration}^*) \times \beta_5 + (\text{Baseline}^*) \times \beta_6$

Bayesian analysis for continuous endpoint	
Population-level coefficients ( $\beta$ )	
 
• <math>\beta</math> = fixed effects, parameters associated to predictors  <math>\beta_k</math>: non-informative prior distributions,  <math>\beta_k \sim \text{Normal}(\text{mean}=0, \text{SD}=100)</math>
 
• Standard deviation <math>\sigma</math>:  Non-informative prior Gamma distribution (shape=2, rate=0.1) (Chung, 2013)
 

\* Unless otherwise specified the predictors (not including study treatment) will be centred around their estimated mean in the model

Further details of primary analysis	
Model diagnostics and checking	
	
 
• Each chain will initially have length Of 1,000,000, thin of 10 and burn-in length of 50,000.
 
• Chain convergence diagnostics will be saved in HARP (refdata folder) and inspected.
 
• The MCSE will be compared with the standard deviation of the posterior distribution (SD) to ensure that only a fraction of the posterior variability is due to simulation error, i.e., the ratio MCSE/SD should be close to 0.01
 

Model results presentation	

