	
 
• The posterior distribution of each arm and the treatment difference (overall and by Advanced Therapy Experience) will be summarized using median and equal-tailed 95% credible region and the probability of being above specific thresholds specified in the programming notes for this output.
 
• Posterior density plots will be available in model output but will not be presented
 

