### 8.2.1.2. Statistical Analysis

Bayesian analysis for binary endpoint	
Endpoints	Endoscopic Mucosal Healing (Endoscopic Improvement)
Statistical analysis	Logistic regression
Predictors	
 
• TRT = study treatment(categorical)
 
• Advanced Therapy Experience (categorical)
 
• Baseline Adapted Mayo (continuous)
 
• Duration of disease, years (continuous)
 

Model	$y_i \sim \text{Ber}(p_i)$ $\text{logit}(p_i) = (\text{TRT}=\text{Placebo}) \times \beta_1 + (\text{TRT}=450\text{mg}) \times \beta_2 + (\text{Duration}^*) \times \beta_3 + (\text{Baseline}^*) \times \beta_4 + (\text{Experience}^*) \times \beta_5$
Outcome	$y_i = \text{response (0/1) for participant } i$
Population-level coefficients ( $\beta$ )	
 
• <math>\beta</math> = fixed effects, parameters associated to predictors  <math>\beta_1</math> : informative prior distribution,  <math>\text{logit}^{-1}(\beta_1) \sim \text{mixture of Betas}^{**}</math>
 
<math>\beta_2</math> : non-informative prior distribution,  <math>\text{logit}^{-1}(\beta_2) \sim \text{Beta}(1/3, 1/3)</math>
 
<math>\beta_k</math> for other predictors: non-informative prior distributions,  <math>\beta_k \sim \text{Normal}(\text{mean}=0, \text{SD}=100)</math>
 

\* Unless otherwise specified the predictors (not including study treatment) will be centred around their estimated mean in the model

\*\* The parameterisation of the priors used in the analysis will be described in [Appendix 14](#): Details of the Informative Placebo Prior and reported in the clinical study report

Further details of key secondary analysis	
Overview of approach	
	
For interim 2 and 3 the predictive probability of meeting the end of study success criteria will be assessed after the Week 10 endoscopy (or withdrawal) has been observed on the number of participants specified for that data cut.
 
A sample from the posterior distribution of the difference in response rates between each treatment arm and placebo will be obtained using Markov chain Monte Carlo (MCMC). This analysis will account for historical placebo data by using an informative prior distribution for the placebo arm and a vague Beta (1/3,1/3) distribution for the active arm (Kerman, 2011).

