### 15.12.6. Efficacy Figures

Efficacy: Figures					
No.	Population	IDSL / Example Shell	Title	Programming Notes	Deliverable [Priority]
Continuous Efficacy					
2.1.	ITTE	EFF_F01	Forest plot of Observed Mayo Score Change from Baseline	By "Overall" then Advanced Therapy Experience level then by endpoint: Complete, Adapted, Partial (at matching timepoint only). Note: categorical axis shows dose level.	SAC
2.2.	ITTE	EFF_F02	Forest plot of Estimated Difference from Placebo in Mayo Score Change from Baseline	By "Overall" then Advanced Therapy Experience level then by endpoint: Complete, Adapted, Partial (Partial at matching timepoint only). Note: categorical axis shows dose level	SAC
2.3.	IIT_ETP	EFF_F01	Forest plot of Observed Mayo Score Change from Baseline – Extended Treatment Phase	By "Overall" then Advanced Therapy level then panelled by endpoint : Complete, Adapted, Partial (Partial at matching timepoint only). Note: categorical axis shows (both) dose levels	None
2.4.	ITTE	Study 200630, Figure 2.5	Mean ( $\pm$ SE) Plot of Partial Mayo Score over time in induction phase	By dose Page by Absolute and Change from Baseline	SAC
2.5.	IIT_ETP	EFF_F01	Forest plot of Observed UCEIS Total Score – Induction Phase	By "Overall" then Advanced Therapy Experience level Note: categorical axis shows dose level	None

Efficacy: Figures					
No.	Population	IDSL / Example Shell	Title	Programming Notes	Deliverable [Priority]
Categorical Efficacy					
2.6.	ITTE	EFF_F03	Forest plot of Proportions for Categorical Endpoints in Induction Phase - Observed	Panel by Endpoint, then Visit, then Dose. Subgroup (within panel) Advanced Therapy Experience level (Note that proportions / odds ratios are on the same scale across endpoints).	IA3H, SAC
2.7.	ITTE	EFF_F04	Forest Plot for Estimated Response Rates for Categorical Endpoints in Induction Phase	Panel by Endpoint, then Visit, then Dose, then rate/delta. Subgroup (within panel) Advanced Therapy Experience level (Note that proportions / odds ratios are on the same scale across endpoints).  Endoscopic Improvement and Clinical Remission	IA3H, SAC

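### By-experience estimates for the binary endpoints are called for, but the only model specified cannot let the treatment effect differ by experience level

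*SAP*

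**What the plan says.** Table 2.21 (SAP 15.12.5) is the model-based analysis of endoscopic improvement and clinical remission in the induction phase, due at the Interim Analysis 3 headline and at the final analysis. Its programming note says "Also report estimate for each level of" advanced therapy experience; in full it reads "Also report estimate for each level of 'Advanced Therapy experience' (i.e. subgroup"). Figure 2.7 (SAP 15.12.6), due at the same two points, is laid out as "Panel by Endpoint, then Visit, then Dose, then rate/delta", with "Subgroup (within panel) Advanced Therapy Experience level".

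The model for endoscopic improvement is the Bayesian logistic regression in SAP 8.2.1.2. Its predictor list gives "Advanced Therapy Experience (categorical") with no mention of an interaction. The linear predictor has one coefficient per arm (β1 placebo, β2 450 mg), then duration, baseline and a centred experience term (β5). SAP 8.2.2 reuses this model for clinical remission.

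The primary continuous model in SAP 8.1.1.2 is different. Its predictor list says "Advanced Therapy Experience (categorical) (includes interaction with study treatment"), its equation has four treatment-by-experience cells, and the results plan says "the treatment difference (overall and by Advanced Therapy Experience) will be summarized using median".

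SAP 5.4.2 lists advanced therapy experience as the only subgroup, for interims and the final analysis, on the ground that it is expected to matter clinically. It gives no model. The stand-alone categorical subgroup analysis (Table 2.22) has deliverable None, which 15.12.3 defines as dropped after the termination decision.

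**The concern.** A table row or forest-plot line labelled naive or experienced invites the reader to ask whether the drug works differently in the two groups. A model without the interaction has already answered that question on the odds-ratio scale before seeing any data. It pools the two groups' treatment effects and re-expresses the pooled effect at two placebo rates. If the drug works in one group only, part of that effect is credited to the other.

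What is at stake is the reading of the one subgroup the SAP keeps, on the endpoint it names as the key secondary for decision making. The SAP gives no reason for treating the binary endpoints differently from the primary endpoint here.

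**Working it through.** The plan states no figure on this point, so there is none to reproduce. The check is algebra followed by illustrations.

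**Algebra.** Under SAP 8.2.1.2, for a given participant profile:

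logit p(placebo) = β1 + duration and baseline terms + β5·experience

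logit p(450 mg) = β2 + the same terms

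The log odds ratio is therefore β2 − β1 at every experience level. Three things follow.

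- The odds ratio, OR = exp(β2 − β1), is common to all levels.
- With fitted placebo rate p0, the active rate is p1 = OR·p0 / (1 − p0 + OR·p0). The difference p1 − p0 has the sign of OR − 1 at every level, and its size varies only through p0.
- In each posterior draw the difference is positive at all levels or at none, so P(difference>0) is identical across levels.

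Using three experience levels instead of two changes none of this.

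**Illustration 1: large-sample fit.** The 2:1 allocation is from the documents (Protocol 6.4.1, SAP 2.3). The naive share and the response rates are assumptions. Priors, duration and baseline are left out.

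Assumed truth: naive 20% placebo and 50% active (+30 points); experienced 10% in both arms (0 points); 40% naive. A main-effects logistic fit must match the response rate in each arm and in each level:

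- placebo: 0.4×20 + 0.6×10 = 14%
- 450 mg: 0.4×50 + 0.6×10 = 26%
- naive: (20 + 2×50)/3 = 40%
- experienced: (10 + 2×10)/3 = 10%

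The fit that does this with a common odds ratio is:

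| Level | Placebo | 450 mg | Difference | True difference |
|---|---|---|---|---|
| Naive | 26.74% | 46.63% | +19.9 | +30 |
| Experienced | 5.51% | 12.25% | +6.7 | 0 |

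Margins: 0.4×26.74 + 0.6×5.51 = 14.0; 0.4×46.63 + 0.6×12.25 = 26.0; (26.74 + 2×46.63)/3 = 40.0; (5.51 + 2×12.25)/3 = 10.0.

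Odds ratios: (46.63/53.37)/(26.74/73.26) = 2.39 and (12.25/87.75)/(5.51/94.49) = 2.39.

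With 20% or 60% naive, the spurious effect in experienced participants is +4.4 or +8.1 points.

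Reversed truth (naive 20% in both arms; experienced 10% to 40%; 40% naive): common OR 2.93, differences +14.7 in naive (truth 0) and +20.2 in experienced (truth +30).

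**Illustration 2: one assumed dataset of interim size.** The 40:20 split is from Protocol 9.2.1. The priors are those of SAP 8.2.1.2, with the 40% naive example from SAP 15.14.1 for placebo. The counts are assumed: naive 2/8 placebo and 9/16 active; experienced 2/12 and 4/24. Duration and baseline are again left out.

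| Model | P(diff>0), naive | P(diff>0), experienced | 95% interval, naive | 95% interval, experienced |
|---|---|---|---|---|
| As in 8.2.1.2 | 0.919 | 0.919 | −0.08 to 0.45 | −0.04 to 0.25 |
| With interaction | 0.951 | 0.562 | −0.06 to 0.64 | −0.24 to 0.23 |

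Observed rates in experienced participants are equal (2/12 = 4/24 = 16.7%), yet the specified model gives them the same P(difference>0) as naive participants.

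**The case against.** Four points on the other side deserve weight.

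First, a reader might infer that the by-level rows certainly come from the no-interaction model. The documents do not settle that. The note to Table 2.21 ends with a parenthesis that equates level with subgroup, and the shell is in a separate document (SAP 15.13), so a separate fit within each stratum cannot be excluded. This stands, and it makes the point conditional. It does not remove it: no per-stratum model is written anywhere, and the stand-alone subgroup table was dropped.

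Second, a reader might infer that the display is bound to show the same effect in both groups. On the rate-difference scale of Figure 2.7 that is not so: the fits above show +19.9 against +6.7, and +14.7 against +20.2. What is forced is the odds ratio, the direction and P(difference>0). The risk is that the mechanical spread is taken for effect modification.

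Third, a reader might infer that heterogeneity would be hidden from the report. It would not. Table 2.17 and Figure 2.6 give observed proportions by experience level at the same two deliverables, and the primary endpoint is reported by experience from a model with the interaction. The limitation is confined to Table 2.21 and Figure 2.7, which could contradict their descriptive counterparts without explanation.

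Fourth, the illustrations use assumed and rather extreme effects, and subgroup cells are small at interim size, so honest intervals are wide. Both are true. Small cells are a reason to show the uncertainty, or to describe only, as SAP 5.4.2 permits. They do not justify narrowing by-level intervals through an unstated common odds ratio.

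**Conclusion.** The point holds in conditional form. The SAP asks for by-experience estimates of two binary endpoints and specifies only a model that cannot estimate separate treatment effects by experience. If that model is used, the by-level rows carry no information on whether the odds ratio differs between levels.

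In the illustration, a true 30-point effect confined to naive participants appears as about +20 in naive and +7 in experienced, and the experienced figure runs from about +4 to +8 as the naive share goes from 20% to 60%. These sizes rest on assumed rates and naive shares and on a large-sample fit without priors or continuous covariates. The equality of odds ratio, direction and P(difference>0) rests on none of these.

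The reach is limited. The overall estimate is not affected. Nor is the Interim Analysis 3 futility calculation, which uses the arm-level response rates and judges end-of-study success without covariates. No decision rule in the documents uses the by-level rows. This is a matter of correct reporting of a subgroup, in a study already terminated.

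**What to change.** For the by-level rows of Table 2.21 and Figure 2.7 only, fit the treatment-by-experience cell form already set out in SAP 8.1.1.2, or a separate fit in each stratum, with vague priors in all cells. The Beta(1/3, 1/3) that the SAP already uses for the active arm is one candidate. State the choice in 8.2.1.2; 8.2.2 then carries it to clinical remission. Keep the current model, with its informative placebo prior, for the overall estimate.

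Do not build subgroup placebo priors by evaluating the historical model at 0% and 100% naive. That model is a regression across whole trials on their share of experienced participants, the historical data are not split by strata (Appendix 14), and the worked examples cover only 20% to 80% naive.

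The cost is an additional model fit per endpoint, cell priors to write down, and a sentence in the SAP. The downside is wider subgroup intervals: in the second illustration, which kept the SAP's informative placebo prior, the experienced interval goes from about 29 points (−0.04 to 0.25) to about 47 (−0.24 to 0.23). If the current model is kept for these rows, the minimum is a footnote saying that they assume one odds ratio across experience levels.

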## CONFIDENTIAL

204869

Efficacy: Tables					
No.	Population	IDSL / Example Shell	Title	Programming Notes	Deliverable [Priority]
2.23.	ITTE	EFF_T3	Statistical Analysis of Dose Response Relationship for Categorical Endpoints	
By Endpoint then estimand.
 
 
• Endoscopic Improvement (IA4 and PC)
 
• Endoscopic Improvement, Clinical Response, Clinical Remission, ( PC only)
 
• Present analysis results for both 'Treatment Policy' and 'Hypothetical' estimands if conducted
 
	None
Histological assessments					
2.24.	ITTE	EFF_T2	Summary of Categorical Histology at each Dose Level by Endpoint in Induction Phase	
Report by endpoint, visit.
 
Geboes Histological Remission
 
RHI Remission
 
RHI Deep Remission
 
Nancy Index Remission
	SAC
2.25.	ITTE ETP	EFF_T2	Summary of Categorical Histology by Endpoint in Extended Treatment Phase	Report by endpoint, visit.	None

Efficacy: Tables					
No.	Population	IDSL / Example Shell	Title	Programming Notes	Deliverable [Priority]
Extra Intestinal Manifestations					
2.26.	ITTE	EFF_T4	Summary of Extra Intestinal Manifestations (EIMs) - Incidents by Severity, across Study Phases.	For EIMs without severity (Peripheral Arthritis and Axial Arthropathy) set levels of severity to missing  Slot early withdrawal visits to next EIM visit (there is one EIM visit at the end of each study phase)  Summary is cross-phase: Report by treatment sequence, not by treatment in an individual study phase	None
Continuous Efficacy – Pairwise Statistical Analysis					
2.27.	ITTE	EFF_T5	Statistical Analysis of Change from Baseline in Complete Mayo Score in Induction Phase		IA3H
Summaries of Efficacy after Estimand Imputations					
2.28.	ITTE	EFF_T2	Summary of Categorical Efficacy by Endpoint in Induction Phase - Estimands		IA3H, SAC
2.29.	ITTE	PD1	Summary of Mayo Score by Endpoint in Induction Phase - Estimands		SAC
2.30.	ITTE	PD1	Summary of UCEIS Total Score in Induction Phase - Estimands		SAC

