	
 • If the four parameter Emax model is not applicable then additional models will be investigated: three parameter Emax model, power model, linear, quadratic, log-transformed dose. Each of the models will be fitted to the data and their fit compared using the Deviance Information Criterion (DIC), where the model with the lowest DIC will be the primary model for inference. • Prior medication will be included as a stratification factor: advanced therapy naïve, experienced a single class of advanced therapy, or experienced multiple classes of advanced therapies. • Further details of the Emax model will be defined in the RAP. • The primary analysis will use the ITTE analysis population. • The primary estimand will use a treatment policy strategy for intercurrent events, with the exception of discontinuations due to COVID-19 pandemic which will use a hypothetical strategy. • Under the hypothetical strategy, data set to missing would be assumed to be missing at random (MAR).
Secondary	
 • Analyses of the secondary endpoints will be conducted using similar methodology as for the primary endpoint (with an appropriate link-function for binary endpoints). • The decision criteria at the interim analyses 3 and following completion of the primary analysis will primarily be based on the proportion of participants who achieve endoscopic healing. These are based on predictive probabilities based on the data available. Details are outlined in Section 9.5, and in the interim analysis charter and RAP.
Exploratory	
 • Will be described in the RAP.

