
 
To investigate the effect of repeat doses of GSK2831781 on UC histologic disease activity during the Double-Blind Induction Phase.
 
	
 
Histological severity as determined by the Robarts Histopathology Index at Week 10.
 
Histological severity as determined by the Nancy Histological Index at Week 10.
 
Histological severity as determined by the Geboes Score at Week 10.
 

 
To investigate the effect of repeat doses of GSK2831781 on biomarkers of UC disease activity during the Double-Blind Induction Phase.
 
	
 
Change from baseline in serum C-reactive protein over time.
 
Change from baseline in faecal calprotectin over time.
 

 
To investigate the pharmacokinetics of GSK2831781 following subcutaneous dosing.
 
	
 
GSK2831781 PK parameters: AUC(0-tau), Cmax, tmax.
 

 
To investigate the immunogenicity of repeat doses of GSK2831781 during the Double-Blind Induction Phase.
 
	
 
Incidence of anti-drug antibodies at each visit.
 

Safety	

 
To evaluate the safety and tolerability of repeat doses of GSK2831781 in all trial phases.
 
	
 
Adverse events, vital signs, clinical laboratory values (haematology, clinical chemistry, and urinalysis), 12-lead ECG.
 

 
To investigate the immunogenicity of repeat doses of GSK2831781 in all trial phases.
 
	
 
Incidence of anti-drug antibodies at each visit.
 

Exploratory	

 
To investigate the effect of repeat doses of GSK2831781 on patient-reported outcomes in all trial phases.
 
	
 
Change from baseline in daily e-Symptom Diary, FACIT-Fatigue, Inflammatory Bowel Disease Questionnaire (IBDQ), SF-36, and PGIS.
 
PGIC at Week 10 and Week 30.
 

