### Robarts Histology Index Conversion from Geboes

CCI - This section contained Clinical Outcome Assessment data collection questionnaires or indices, which are protected by third party copyright laws and therefore have been excluded.

The RHI Score is a continuous score, ranging from 0-33 with higher scores indicating more severe disease. The following categorical endpoints are derived from this score:

- “**RHI Remission**” will be defined as an RHI score  $\leq 6$
- “**RHI Deep Remission**” will be defined as an RHI score  $\leq 3$

[figure not shown]

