## CONFIDENTIAL

204869

Non-ICH: Listings					
No.	Population	IDS / Example Shell	Title	Programming Notes	Deliverable [Priority]
Medical History / Concomitant Medications					
45.	ITTE	POP_L3	Listing of Ulcerative Colitis Disease Characteristics at Baseline		IA3H, SAC
46.	ITTE	POP_L4	Listing of Ulcerative Colitis Therapeutic History		IA3H, SAC
Efficacy					
47.	ITTE	EFF_L1	Listing of Mayo Score		None
48.	ITTE	EFF_L1	Listing of UCEIS Total Score		None
49.	ITTE	EFF_L2	Listing of Corticosteroid Use During Mandatory Taper in Extended Treatment Phase and Open Label Extended Treatment Phase		None
50.	ITTE	EFF_L3	Listing of Categorical Efficacy		None
51.	ITTE	EFF_L3	Listing of Categorical Histology		None
52.	ITTE	EFF_L4	Listing of Extra Intestinal Manifestations (EIMs)		None
Pharmacokinetic					
53.	PK	PK07xo	Listing of Plasma GSK2831781 Concentration-Time Data		SAC
54.	PK	PK13xo	Listing of Derived Plasma GSK2831781 Pharmacokinetic Parameters		SAC
Biomarker					
55.	ITTE	PK07xo	Listing of Plasma sLAG3 Concentration-Time Data		None
56.	ITTE	BIO_L1	Listing of Flow Cytometry		None
57.	ITTE	BIO_L1	Listing of Colon Biopsy Cell Counts		IA3, SAC
58.	ITTE	BIO_L1	Listing of Disease Biomarkers		None
Patient Reported Outcome					
59.	ITTE	PRO_L1	Listing of Reported Symptom Control		None

Non-ICH: Listings					
No.	Population	IDS / Example Shell	Title	Programming Notes	Deliverable [Priority]
60.	ITTE	PRO_L2	Listing of SF-36		None
61.	ITTE	PRO_L2	Listing of IDBQ		None
62.	ITTE	PRO_L2	Listing of Facit-Fatigue		None
63.	ITTE	PRO_L3	Listing of PGIS		None
Population PK					
64.	PK		PK and sLAG3 data excluded from population PK modelling	To be generated by CPMS	SAC
65.	PK		Text output of final PK model (lst-file)	To be generated by CPMS	SAC
PK / PD					
66.	ITTE		PD data excluded from population PK/PD modelling	To be generated by CPMS	SAC
67.	ITTE		Text output of final PK/PD model (lst-file)	To be generated by CPMS	SAC
Estimands and Intercurrent Events					
68.	ITTE	EFF_L5	Listing of Intercurrent Events		IA3H, SAC
69.	ITTE	EFF_L6	Listing of Estimand Imputations for Efficacy		IA3H
COVID-19 Pandemic					
70.	Safety	PAN12	Listing of COVID-19 Assessments and Symptom Assessments		SAC

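### Week 10 histological severity is a declared secondary endpoint on three scales, but the final outputs report only remission categories and the SAP does not record this

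*SAP*

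**What the plan says.** SAP Section 2.2 keeps three secondary histology endpoints: "Histological severity as determined by the Robarts Histopathology Index at Week 10", "Histological severity as determined by the Nancy Histological Index at Week 10" and "Histological severity as determined by the Geboes Score at Week 10". Protocol Section 3 lists the same three, under a slightly different name for Geboes. For secondary endpoints in general, Protocol Section 9.4.1 states: "Analyses of the secondary endpoints will be conducted using similar methodology as for the primary endpoint".

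SAP Section 15.6.3.4 describes the RHI in these words: "The RHI Score is a continuous score, ranging from 0-33 with higher scores indicating more severe disease". It then defines two categories from it: remission at a score of 6 or less, and "RHI Deep Remission" at 3 or less.

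In SAP Section 15.12.5 the only histology table assigned to the final analysis is Table 2.24, "Summary of Categorical Histology at each Dose Level by Endpoint in Induction Phase". Its programming note names Geboes remission, RHI remission, RHI deep remission and Nancy remission. Table 2.25 is the categorical counterpart for the extended treatment phase, and its deliverable is None. In Section 15.12.20, Listing 51, "Listing of Categorical Histology", is also marked None.

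**The concern.** The declared question is how severe the histological disease is at Week 10. The planned output answers a different one: how many participants fall below a remission threshold. A reader of the study report would look for the score and not find it, and the SAP would not say why. SAP Section 2.1.3.1 declares only exploratory efficacy endpoints as dropped after termination, and these are secondary.

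The gap also sets histology apart from comparable endpoints. UCEIS and the Adapted Mayo endoscopic score are Week 10 secondary scores too, and both keep score-level summaries. What is at stake is the ability to see a partial histological improvement, in a trial whose early termination already limits the data.

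**Working it through.** The documents give no sample size, rate or standard deviation for histology, so there is no figure of the plan's own to reproduce. The check has three steps.

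**1. Endpoints against outputs.** Declared Week 10 secondary scores, set against SAP Sections 8.2.2, 8.2.3, 15.12.5, 15.12.6 and 15.12.20:

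| Scale | Listed in 8.2.2 or 8.2.3 | Score-level table for the final analysis | Categorical table for the final analysis |
|---|---|---|---|
| UCEIS | yes | 2.8 and 2.30 | none |
| Adapted Mayo endoscopic score | yes | 2.2 | 2.17 |
| RHI | no | none | 2.24, two cuts |
| Nancy | no | none | 2.24, remission |
| Geboes | no | none | 2.24, remission |

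Three of three declared histology endpoints have no score-level output. The general summary rule at the start of SAP Section 8 does not fill the gap. It covers variables defined in that section, and the histology scores are defined in Appendix 6. SAP Section 2.1.4 says that new estimands are defined for the secondary continuous and categorical efficacy endpoints, yet histology appears in neither list.

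**2. What the RHI categories can show.** With cuts at 6 and 3 on a 0 to 33 scale, every score above 6 falls into one category. A participant who falls from 20 to 10 (hypothetical values) is counted the same as one who stays at 20.

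**3. Size, for RHI only.** Assume a normally distributed score and a small shift between arms. Let p be the share in remission, z_p the normal quantile at p and φ the standard normal density. The efficiency of comparing remission proportions, relative to comparing mean scores, is φ(z_p)² / [p(1 − p)]. The values of p are assumed.

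| p | φ(z_p) | Efficiency | Information lost |
|---|---|---|---|
| 10% | 0.1755 | 0.0308 / 0.09 = 0.342 | 66% |
| 20% | 0.2800 | 0.0784 / 0.16 = 0.490 | 51% |
| 30% | 0.3477 | 0.1209 / 0.21 = 0.576 | 42% |
| 50% | 0.3989 | 0.1592 / 0.25 = 0.637 | 36% |

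More than half is lost only if p is below about 21% or, by symmetry, above about 79%.

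Table 2.24 gives RHI at two cuts. With cumulative shares p1 (score 3 or less) and p2 (score 6 or less), the efficiency of the three ordered levels is φ1²/p1 + (φ2 − φ1)²/(p2 − p1) + φ2²/(1 − p2). For 10% and 20%:

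0.1755²/0.10 + (0.2800 − 0.1755)²/0.10 + 0.2800²/0.80 = 0.308 + 0.109 + 0.098 = 0.515.

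The same formula gives 0.352 for 5% and 10%, 0.629 for 10% and 30%, and 0.697 for 20% and 40%. The loss over this range is about 30% to 65%. At each remission rate it is somewhat smaller than with the single cut.

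**The case against.** The strongest reply is that remission summaries were always foreseen. Protocol Section 8.2.2 defers the definitions of histological remission to the analysis plan. The Week 10 endpoint also states no summary measure, whereas the exploratory Week 22 and Week 30 endpoints explicitly ask for change from baseline. That makes Table 2.24 legitimate content. It does not make remission the declared endpoint, and nothing in either document says that remission stands in for severity.

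Several stronger readings are tempting, and the documents do not support them:

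- A reader might infer that the endpoint is not delivered at all. Each scale does get a categorical Week 10 summary. What is missing is severity as a score.
- A reader might infer that most of the information is lost. That depends on a histological remission rate, which the documents do not give. At 30% and 50% more than half is kept, and RHI has two cuts.
- A reader might extend the efficiency figures to Nancy and Geboes. Only RHI is described as continuous. The scoring text for the other two is blacked out, and no numeric Geboes total is visible.
- A reader might infer that a score table was planned and then withdrawn. SAP Section 15.12.3 marks displays removed after termination as None, and no histology score table appears among them.

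It is also fair to say that relative efficiency has limited practical weight here. The SAP plans no formal histology comparison, and it only summarises several other secondary endpoints, including UCEIS. The mock shells are in a separate document, so the layout of Table 2.24 cannot be checked. Its title and programming note name only categories.

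**Conclusion.** The point stands as a mismatch between three declared secondary endpoints and their output, and the SAP's list of changes does not record it. That conclusion needs no calculation and rests only on the endpoint lists and the display lists. Followed as written, the plan gives no histological severity score at Week 10 on any scale, and improvement that stays above a cut-point is invisible.

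The size is illustrative and applies to RHI alone: about 36% to 66% of the information lost with one cut at remission rates of 50% to 10%, and somewhat less with both cuts. It assumes normality on a bounded scale, a small shift and assumed remission rates.

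**What to change.** Add RHI and Nancy, and Geboes where a numeric score is defined, to the continuous secondary endpoints in SAP Section 8.2.3, so that the primary estimand's intercurrent-event rules apply to them as to the others. Add one descriptive table to Section 15.12.5, of the PD1 type already used for UCEIS, giving the Week 10 value and change from baseline by arm. Keep Table 2.24 as supportive.

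A 450 mg minus placebo difference adjusted for baseline, with a 95% interval, is optional, because it would exceed what UCEIS receives. If the sponsor prefers to report remission only, SAP Section 2.1.3.1 should say so and give the reason.

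The cost is one additional table and no new data. Biopsies are scheduled at screening and Week 10, RHI is derived from Geboes sub-scores, and the Nancy index is supplied by the external reader.
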